## **16.7. Record Retention**

All pertinent data, samples, photographs, correspondence, original or amended protocol, reports and all other material relating to the study will be maintained securely in Aclaris Therapeutics, Inc./CRO/investigator archives for the legally required duration for archiving.

The investigator should maintain the essential study documents as specified in ICH GCP, and in compliance with all regulatory requirements. The investigator should ensure these documents are protected from accidental destruction or disposal.

If the Investigator needs to re-assign responsibility for maintaining these documents (*e.g.*, due to retirement) it must be transferred to a person willing to accept this responsibility. The

Aclaris Therapeutics, Inc.

Protocol Number: A-101-WART-301

Amendment 3: Version 5 14 February 2019

investigator must notify Aclaris Therapeutics, Inc., in writing, of the name and address of the new individual.

If the Investigator cannot guarantee this archiving requirement at the investigative site for any or all of the documents, special arrangements must be made between the Investigator and the Sponsor to store these in sealed containers in an off-site storage location so that they can be returned to the Investigator in case of a regulatory audit. Where source documents are required for the continued care of the patient, appropriate copies will be made for off-site storage.

No trial document should be destroyed without prior written agreement between the Sponsor and the Investigator. Should the Investigator wish to assign the trial records to another party or move them to another location, the Investigator must notify the Sponsor in writing of the new responsible person and/or the new location.

## **17. ETHICS AND GENERAL STUDY CONDUCT CONSIDERATIONS**

### **17.1. Institutional Review Board (IRB)/Ethics Committee (EC)**

This protocol and any accompanying material, including information that will be provided to prospective patients (such as advertisements, patient information sheets, or study descriptions used to induce study participation or obtain informed consent) must be submitted to the Central IRB for approval. Approval of each such submission must be obtained from the committee before it may be used in the study and must be documented in a written notification to the Investigator specifying the protocol number, protocol version, documents reviewed, and date on which the committee met and granted the approval. In particular, each informed consent document must bear clear evidence (written, stamp, date of approval, etc.) of IRB approval before it may be presented to prospective (or ongoing, as appropriate) study patients for signature.

Written evidence of the approval must be made available to the Sponsor. Any modifications made to the protocol and of correspondingly modified informed consent documents made after receipt of Central IRB approval must also be submitted to the committee for approval before implementation unless the modification is made on an emergency basis to protect the welfare of study patients. In the latter case, the Central IRB must be notified promptly and their written approval must be obtained as soon after the fact as possible.

Appropriate reports on the progress of the study will be made to the Central IRB and the Sponsor by the Investigator in accordance with applicable regulatory regulations and in conformity with policies established by both the Central IRB and the Sponsor. The shortest time interval between required reports required by either party or by regulations will prevail.

The Investigator at each investigative site, or his/her nominee, will be responsible for reporting any SAEs to the Central IRB as soon as possible, and in accordance with the guidelines of the Central IRB.

The Sponsor will be responsible for reporting all serious, life threatening or fatal adverse study drug events with a causal relationship to the study drug to appropriate regulatory agencies within their required timelines.

The Investigator is responsible for obtaining written, informed consent(s) from each prospective patient interested in participating in this study before performing any study-related procedures. Written informed consent must be obtained after adequate, thorough, and clear explanation of the aims, methods, objectives, and potential hazards of the study, as well as any use of the patient's genetic information from the study. The Investigator must use the most current Central IRB-approved consent form for documenting written informed consent. Each informed consent will be appropriately signed and dated by the patient and the person obtaining consent and each page not signed must be initialed and dated by the patient. The investigational site must retain the original signed consent and provide a copy to the patient.

## **17.2. Ethical Conduct of the Study**

The Sponsor will use information developed in this clinical study in connection with the development of A-101 Solution and, therefore, may disclose it as required to other clinical Investigators participating in other studies and to regulatory agencies. In order to allow the use of the information derived from this clinical study, the Investigator understands that he/she has an obligation to provide all data produced during this study to the Sponsor.

The Sponsor considers that clinical data (complete or incomplete) constitute financially sensitive information. Consequently, the Sponsor requires that discussion of results in any form, electronic, verbal, or written before study completion and full reporting should only be undertaken with the Sponsor's prior written consent.

Individual patients' medical information obtained as a result of this study is considered confidential. The Investigator and the study center will adhere to all applicable laws relating to the protection of patient information. To assure that patients' confidentiality is maintained, patients' data will be identified by a study-assigned number.

All Sponsor personnel will handle patients' data in a confidential manner in accordance with applicable regulations governing clinical research. Subjects' records will be inspected only in connection with this research project. Information generated as a result of a subject's participation in this study may be disclosed to third parties for research and regulatory purposes in any country as determined by the Sponsor. However, subjects will not be individually identified but will be referred to only by the study assigned number.

## **17.3. Regulatory Documents**

The investigator must maintain a study file containing current and complete regulatory documentation in compliance with the current ICH E6 GCP guideline. This file will be reviewed as part of the routine monitoring for this study.

## **17.4. Contractual Requirements**

A contractual agreement will be signed between Aclaris Therapeutics, Inc. and each investigator. This document will contain supplemental information, including financial terms, confidentiality, study schedule, third party responsibility, and publication rights.

## APPENDIX 1. A-101-WART-301 SUBJECT INSTRUCTION SHEET

Please follow these instructions carefully. Contact the study staff at the telephone number noted below if you have any questions about the study:

Contact: \_\_\_\_\_ Telephone: \_\_\_\_\_

### THROUGHOUT THE STUDY:

- Continue your routine cleansing regimen except avoid vigorous scrubbing of the identified common warts (*e.g.*, abrasive cleansing pads, abrasive cleansers, etc.).
- Continue your routine skin care products.
- Avoid exposing the identified common warts to excessive natural or artificial ultraviolet radiation (*e.g.*, sunlight, tanning beds) and use sunscreen on the wart, if excessive exposure cannot be avoided.
- Avoid activities that might irritate the identified common warts.
- Bring this subject instruction sheet and subject diary with you to each visit.

### STARTING WITH VISIT 2:

- On visit days, do not apply any topical products (*e.g.*, moisturizers, sunscreens) to the identified common wart, except for routine cleansing products, within **12 hours** prior to the visit
- After any study visit where a study medication treatment occurred **DO NOT:**
  - Wash/submerge the treated common warts for at least **6 hours** after the treatment
  - Apply any topical products to the treated common warts for at least **6 hours**
  - Occlude, bandage or otherwise cover the common wart treatment area (loose-fitting clothing is permissible) for at least **6 hours**.

Parents/legal guardians of children must ensure that the child does not put the treated area in their mouth, or eyes, until completely dry after the application. If the treated area is not completely dry 10 minutes after the application, the area should be blotted dry.

**STUDY MEDICATION:** The study medication provided to you is only to be used as instructed.

Please ask your doctor or staff if you have any questions about its use.

### STUDY VISIT SCHEDULE:

VISIT 2:	VISIT 3:
----------	----------

Date:                      Time:	Date:                      Time:
VISIT 4: Date:                      Time:	VISIT 5: Date:                      Time:
VISIT 6: Date:                      Time:	VISIT 7: Date:                      Time:
VISIT 8: Date:                      Time:	VISIT 9: Date:                      Time:
VISIT 10: Date:                      Time:	VISIT 11: Date:                      Time:
VISIT 12: Date:                      Time:	VISIT 13: Date:                      Time:

**At Home Study Administration Days:**

- Do not apply any topical products (*e.g.*, moisturizers, sunscreens) to the identified common wart, except for routine cleansing products, within **12 hours** prior to the administration.
- After application of the study medication do not:
  - Wash/submerge the treated common wart for at least **6 hours** after the treatment
  - Apply any topical products to the treated common wart for at least **6 hours**
  - Occlude, bandage or otherwise cover the common wart treatment area (loose-fitting clothing is permissible) for at least **6 hours**.

[figure not shown]
Parents/legal guardians of children must ensure that the child does not put the treated area in their mouth, or eyes, until completely dry after the application. If the treated

area is not completely dry 10 minutes after the application, the area should be blotted dry.

**At Home Study Medication Application:**

- Wash your hands prior to completing study medication treatment.
- Visually inspect the applicator for damage. If the applicator appears damaged do not use it for the treatment.
- Do not apply the study medications to eyes, nose, mouth, mucous membranes, or open wounds.
- Wear nitrile examination gloves during the treatment that were provided to you by your doctor. Latex gloves are prohibited
- Thoroughly cleanse the identified common wart by firmly rubbing with a swab/wipe wetted with 70% isopropyl alcohol that was provided to you by your doctor.
- Using firm pressure and with the tip of the applicator held over the wart, squeeze in the middle of the applicator to apply one drop of study medication onto the identified common wart. Using the smaller side of the applicator tip, firmly move the applicator around in a circular motion to fully saturate the lesion. Apply the study medication for approximately 15 seconds.
- Minimize exposure to the surrounding normal skin.
- During the treatment process remove excess study medication from the surrounding skin using a clean absorbent wipe.
- Ensure the each identified wart is fully saturated with study medication at the end of the approximately 15 second application.
- Allow the treated wart to remain undisturbed for approximately 15 seconds.
- After approximately 15 seconds repeat the approximately 15 second application process.
- Repeat the application/waiting cycle until the study medication has been applied to the identified common wart up to 3 times.
- Absorb any remaining A-101 study medication and dry the treated common wart and the surrounding skin without wiping or rubbing.
- Document, in your treatment diary, the number of times the identified common wart is treated during a treatment.
- After applying the study medication, the cap should be put back on the applicator, the used applicator should be put in one of the used nitrile gloves (after removal), knotted at the end and placed in a biohazard bag. The biohazard bag, with the used applicator in the glove, should be placed in the plastic bag you brought the applicator home in, and returned to the site for accountability.

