**Study Drug Administration**

Study drug medication will be applied to each identified common wart which meets the requirements for retreatment twice a week for up to 8 weeks (maximum of 16 applications). At Visit 2, subjects

Aclaris Therapeutics, Inc.

Protocol Number: A-101-WART-301

Amendment 3: Version 5 14 February 2019

who are 18 years of age or older will apply the A-101 study medication in the presence of the treating physician or a member of the investigational site staff who is a trained healthcare professional. The second weekly application of the A-101 study medication will be applied by the subject at home. Subjects between the ages of 1 and 17 years of age will have their A-101 study medication applied in the office by a parent or legal guardian in the presence of the treating physician or a member of the investigational site staff. The second weekly A-101 study medication application will be applied at home by a parent or a legal guardian.

Study medication must be applied to each identified common wart for approximately 15 seconds. The treated wart must remain undisturbed for an additional approximately 15 seconds. This treatment cycle must be repeated up to 3 times to the common wart. If severe erythema and edema develop, then the treatment cycle should be discontinued for that specific treatment application.

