**Table 2: Study Procedures**

Visit	V1 Screening	V2	V3	V4	V5	V6	V7	V8	V9	V10	V11	V12	V13
Treatment Day	-13 to 0	1	8	15	22	29	36	43	50	60	78	106	137
Treatment Window	N/A	N/A	±1 day	+4 days	±7 days	±7 days	+7 days						
Study Procedures													
Informed Consent	▲												
Inclusion Criteria/Exclusion Criteria	▲	▲ 											
Subject Identifier	▲ 												
Medical history/demographics	▲												
Fitzpatrick Skin Type Assessment	▲ 												
Vital Signs	▲ 								▲				▲
Prior Medications/Therapies	▲ 												
Clinical Chemistry and CBC 	▲												▲
Common Wart Identification 	▲												
Physician's Wart Assessment 	▲	▲	▲	▲	▲	▲	▲	▲	▲	▲	▲	▲	▲

Visit	V1 Screening	V2	V3	V4	V5	V6	V7	V8	V9	V10	V11	V12	V13
Treatment Day	-13 to 0	1	8	15	22	29	36	43	50	60	78	106	137
Treatment Window	N/A	N/A	±1 day	±1 day	±1 day	±1 day	±1 day	±1 day	±1 day	+4 days	±7 days	±7 days	+7 days
Common Wart Dimensions 	▲	▲	▲	▲	▲	▲	▲	▲	▲	▲	▲	▲	▲
Standardized Photography 	▲	▲ 		▲		▲			▲	▲	▲	▲	▲
Subject Randomization		▲ 											
Local Skin Reactions		▲ 	▲ 	▲ 	▲ 	▲ 	▲ 	▲ 	▲	▲	▲	▲	▲
Study Medication Application 		▲	▲	▲	▲	▲	▲	▲	▲				
Study Medication Application at Home 			A-101 Study Medication will be applied at home on Days 4, 11, 18, 25, 32, 39, 46, 53. A window of +1 day is allowed.										
Subject Instructions	▲	▲	▲	▲	▲	▲	▲	▲	▲	▲	▲	▲	
Concomitant therapies 		▲	▲	▲	▲	▲	▲	▲	▲	▲	▲	▲	
Adverse Events 		▲	▲	▲	▲	▲	▲	▲	▲	▲	▲		

Subject inclusion/exclusion criteria will be re-assessed prior to randomization during Visit 2.

Investigational sites will assign a unique five-digit subject identifier to each subject at Visit 1. This subject identifier will be used in all study documentation for the duration of the study.

Each subject’s skin must be assessed during Visit 1 using the Fitzpatrick Skin Type Assessment.

Aclaris Therapeutics, Inc.

Protocol Number: A-101-WART-301

Amendment 3: Version 5 14 February 2019

Vital signs [including temperature, pulse, respiratory rate, blood pressure, height and weight (Visit 1 only)] will be measured by a qualified staff member at Visit 1, Visit 9 and Visit 13.

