 The investigator and subject will assess each identified common wart for local skin reactions associated with irritation at Visits 2-13. At Visit 2-Visit 9, the investigator and subject will assess each identified common wart for LSRs prior to the application of the study medication. Refer to Section 13.1 for the complete list of Local Skin Reaction signs and symptoms.

During in-office visits, subjects 18 years of age and older will apply their A-101 study medication in the presence of the treating physician or a member of the investigational study staff that has been trained on the protocol. Subjects ages 1 to 17 will have their A-101 study medication applied by a parent/legal guardian in front of the treating physician or a member of the investigational study staff during in-office visits. If the identified common wart meets the criteria

Aclaris Therapeutics, Inc.

Protocol Number: A-101-WART-301

Amendment 3: Version 5 14 February 2019

for re-treatment as defined in Section 10.6 the lesion will be re-treated at Visits 3-9. Following application of study medication, subjects must NOT wash/submerge the treated wart for at least 6 hours and they must NOT apply any topical products to the treated common warts for at least 6 hours. Parents/legal guardians of children must ensure that the child does not put the treated area in their mouth, or eyes, until completely dry after the application. If the treated area is not completely dry 10 minutes after the application, the area should be blotted dry.

All subjects will receive their second weekly treatment of the A-101 study medication at home on Days 4, 11, 18, 25, 25, 32, 39, 46, 53 as determined by the PWA assessment performed during the in-office visit. Subjects ages 1 to 17 will have their A-101 study medication applied by a parent or legal guardian. All subjects will need to document the application of A-101 study medication in a subject diary. The second weekly treatment will depend on the PWA performed during the in-office visit that week. If the identified common wart meets the criteria for re-treatment during the in-office visit, then the subject/parent/guardian will perform the second weekly treatment at home.

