**Retreatment Criteria:**

At Visit 3-9, if the identified common wart has a **PWA grade of >0** then the subject will receive re-treatment with the A-101 study medication treatment. However, treatment with the A-101 study medication should not be applied if any of the following criteria apply to the identified common wart:

- The common wart has a pre-treatment LSR grade of 3 (severe) for any sign or symptom AND the grade has increased compared to the previous visit.
- The common wart is, in the investigator's opinion, not appropriate for a retreatment (the investigator must note the reason on the subject's Comments CRF page).
- The common wart, in the Investigator's opinion, cannot be visualized so the Investigator cannot assess the PWA.

If the identified common wart meets the criteria for re-treatment during the in-office visit (PWA>0), then the subject/parent/legal guardian should treat the common wart at home on the protocol defined at home treatment days (Days 4, 11, 18, 25, 32, 39, 46, 53. A window of +1 day is allowed). If the subject is unable to tolerate treatment the day of an at home treatment visit due to severe skin irritation, then the treatment should be held and the investigational site should be notified.

Subjects whose identified common wart(s) is assessed at a particular visit (V3-V9) to be a PWA=0 will not have the that common wart re-treated at that visit (or retreated at the second at home application that week).

[figure not shown]

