## 10.7. Applying Study Medication

All subjects that are between the ages of 1 and 17 will have their A-101 study medication applied by a parent/legal guardian. Parents/legal guardians of children must ensure that the child does not put the treated area in their mouth, or eyes, until completely dry after the application. If the treated area is not completely dry 10 minutes after the application, the area should be blotted dry. . For in-office visits, the subject's parent or legal guardian will apply the A-101 study medication in front of a member of the investigational study staff to ensure there is a clear understanding regarding how the study medication should be handled.

Subjects 18 years of age and older will apply their A-101 study medication to his/her identified common warts in the presence of the treating physician or member of the investigational staff during in-office visits. The second weekly application will be performed at home.

The following instructions will be used by all subjects/parents/legal guardians applying A-101 study medication to all identified common warts:

- Do not apply the study medications to eyes, nose, mouth, mucous membranes, or open wounds
- Wear nitrile or vinyl examination gloves during the treatment; **latex gloves are prohibited (All subjects will be supplied with nitrile or vinyl examination gloves to be used for at home applications)**
- Thoroughly cleanse the common wart by firmly rubbing with a swab/wipe wetted with 70% isopropyl alcohol
- Using firm pressure and with the tip of the applicator held over the wart, squeeze in the middle of the applicator to apply one drop of study medication onto the common wart. Using the smaller side of the applicator tip, move the applicator around in a circular motion to fully saturate the lesion. Apply the study medication for approximately 15 seconds.
- Minimize exposure to the surrounding normal skin
- During the treatment process remove excess study medication from the surrounding skin using a clean absorbent wipe.
- Ensure the identified common wart is fully saturated with study medication at the end of the ~15 second application
- Allow the treated wart to remain undisturbed for ~15 seconds
- After ~15 seconds repeat the ~15 second application process
- Repeat the application/waiting cycle until the study medication has been applied to each identified Wart up to 3 times.

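### The Appendix 1 home-application list leaves out two skin-reaction rules that the protocol body sets: stop the cycle for severe erythema and edema, and hold a home dose and tell the site for severe irritation

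*Protocol*

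**What the plan says.** Section 10.7 introduces its application steps with "The following instructions will be used by all subjects/parents/legal guardians applying A-101 study medication to all identified common warts". The list covers home use, since it refers to gloves supplied for that purpose. After the step that limits the cycles to three, it adds the stop rule, worded as in the Synopsis under Study Drug Administration: "If severe erythema and edema develop, then the treatment cycle should be discontinued for that specific treatment application".

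Section 10.5, under Retreatment Criteria, has a rule written for home treatment days. If severe skin irritation means the subject cannot tolerate treatment that day, "then the treatment should be held and the investigational site should be notified".

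Section 12.4 has staff give each subject the Subject Instruction Sheet at Visit 1, refers to Appendix 1 for it, and asks subjects to bring it to each visit. The home-application list on that sheet says "Repeat the application/waiting cycle until the study medication has been applied to the identified common wart up to 3 times". Its next step is to absorb the remaining solution and dry the wart.

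**The concern.** The sheet is the one document shown in the protocol that is addressed to the person dosing at home. It copies the Section 10.7 sequence but not the step that says when to stop, and it does not carry the home-day rule from Section 10.5. A parent who follows the sheet as written has a ceiling on the number of cycles, but no instruction to stop early for a severe reaction, to skip a dose, or to report severe irritation.

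Both rules matter most when no staff are present. The product is 45% hydrogen peroxide, eligibility starts at age 1, and about 100 of about 500 subjects are to be aged 1 to 17. What is at stake is the skin safety of a probably small number of subjects, not the trial's inference.

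**Working it through.** The plan states no figure on this point, so the check is a comparison of texts.

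**Stop rule: Section 10.7 against the Appendix 1 home-application list.**

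| Section 10.7 step | In Appendix 1? |
|---|---|
| 1. Keep away from eyes, nose, mouth, mucosa, open wounds | Yes |
| 2. Wear gloves, no latex | Yes (nitrile only) |
| 3. Cleanse with isopropyl alcohol | Yes |
| 4. Apply one drop and work it in for about 15 seconds | Yes |
| 5. Limit contact with normal skin | Yes |
| 6. Remove excess during treatment | Yes |
| 7. Check the wart is saturated | Yes |
| 8. Leave for about 15 seconds | Yes |
| 9. Repeat the 15-second application | Yes |
| 10. Up to 3 cycles | Yes |
| 11. Stop the cycle for severe erythema and edema | **No** |
| 12. Absorb the remainder and dry | Yes |

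Eleven of the 12 steps are carried over. The one missing is the stop rule, which sits between two steps that are both present. The sheet also adds lines of its own on hand washing, applicator damage, the diary and disposal.

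**Hold-and-notify rule: Section 10.5 against all readable text of Appendix 1.** The parts read were the contact line, the advice for the whole study, the instructions from Visit 2, the medication statement, the visit calendar, the home-day instructions, the application list and the preparation steps. None tells the reader to withhold a dose or call the site for severe irritation. The contact line is for questions about the study, and the medication statement sends questions about use to the doctor or staff.

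**Does the stop rule reach home dosing?** It is not labelled home-only. However, Section 10.7 applies its list to everyone who applies the drug, so it does.

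**Exposure.** The maximum is 16 applications. Eight are in the office (Visits 2 to 9), which leaves 16 − 8 = 8 at home, matching the 8 home days listed in Section 7. Rules carried onto the sheet: 0 of 2.

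**Would the sheet be expected to carry such rules?** The caution about keeping a treated area out of a child's mouth and eyes stands in both Section 10.7 and Appendix 1, and Section 1.1 shows it was added to both in the same version. So the sheet is already used for home-safety rules.

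**The case against.** The strongest reply is that the body already contains both rules and nothing requires Appendix 1 to repeat it in full. Section 10.6 has staff review the instructions at every office treatment visit and make sure they are understood. Under Section 10.7 the person who doses at home also doses in front of staff. The sheet gives a telephone line, and a worried parent could use it. Phase 2 local reactions were predominantly mild and transient (Section 5.2).

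Most of this stands, and it is why the point is minor. It does not close the gap. The Section 10.6 review concerns preparing and applying the drug and points to the instructions that follow it. The hold rule comes earlier, in Section 10.5, and is not expressly covered. A line for questions does not tell a parent to withhold a dose.

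Three stronger readings are tempting and not supported:

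- *The sheet contradicts the body.* It does not. A limit of up to three cycles permits fewer, so the sheet is incomplete.
- *Families have neither rule in writing.* This cannot be established. Section 10.6 also mentions treatment application instruction sheets supplied after each office visit, and the text does not say whether these are Appendix 1. A figure in the home-day part of Appendix 1 is not shown, and neither is the diary.
- *The local skin reaction (LSR) bar screens a definite share of home doses, or none.* The office bar applies where a wart "has a pre-treatment LSR grade of 3 (severe) for any sign or symptom AND the grade has increased compared to the previous visit". For the home dose the text says "The second weekly treatment will depend on the PWA performed during the in-office visit that week". Whether the bar carries over to the home dose is not stated, so no count of screened home doses can be given.

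**Conclusion.** The point holds as a minor safety inconsistency. The stop rule is certainly absent from the Appendix 1 home-application list, because that list is complete as text. The hold-and-notify rule is absent from the readable text of Appendix 1; that statement is limited by the figure that cannot be seen.

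The size is 0 of 2 rules on the sheet, bearing on up to 8 of 16 applications per subject. The number of severe reactions is not given in the protocol. On the Phase 2 description it is probably small, which is an inference and not a calculation.

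A reader might go on to infer an effect on the primary endpoint, the analysis or adverse event reporting. Nothing in the protocol supports that, and none is claimed.

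**What to change.** In the home-application list of Appendix 1, directly after the step that limits the cycles to three, add:

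- *If severe redness and swelling develop, stop the treatment cycle for that application.*
- *If severe skin irritation means you cannot tolerate treatment on a home treatment day, do not treat, and call the study staff at the number on this sheet.*

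Widen the contact line at the top of the sheet so that it also covers severe skin irritation. If the instruction sheets mentioned in Section 10.6 are a different document, make the same additions there.

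The cost is a few lines of text. The revised sheet needs IRB approval under Section 17.1. It may also need a written protocol amendment under Section 16.1; an earlier change to this sheet was made by amendment (Section 1.1). No visits, staff or data fields are added.
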